Outcomes	
Primary Efficacy Outcome The primary endpoint is incidence of clinical response, defined by at least 50% reduction on the HAM-D₁₇ total symptom scores from Baseline through 6 weeks of treatment.
 
Additional Efficacy Outcomes
 
 • The change in mean total symptom scores on the HAM-D₁₇ through 6 weeks of treatment • The change in mean total symptom scores on the MADRS through 6 weeks of treatment. 
Safety Outcomes Safety will be assessed by the following:
 
 • The incidence and severity of all adverse events (including, but not limited to, serious adverse events and device-related adverse events) • Changes in Columbia Suicide Severity Rating Scale (C-SSRS) • Adequacy of blinding will be assessed using a Blinding Questionnaire administered at the Week 1 and Week 6 clinical assessment visits.
Statistical Methodology	
The primary efficacy analysis will be performed on both the ITT and evaluable Per Protocol subgroup, with results from the Per Protocol analysis used for confirmation of the previous NEST study results. The incidence of clinical response, defined as a reduction in HAM-D₁₇ \geq 50% at 6 weeks will be the primary efficacy outcome measure. The sample size estimation for this confirmatory study is based on the treatment resistant population results from the original NEST study, which demonstrated a 34% response rate for sTMS versus 8% for Sham treatment for the Per Protocol population. Assuming

true population response rates of 34% for sTMS and 8% for Sham, power analysis indicates that a sample size of 92 evaluable (Per Protocol) subjects (46 subjects per treatment group evaluable at week 6) yields 81% power to demonstrate superiority of sTMS over Sham, where the statistical test is Fisher's exact test at a two-sided 0.05 level of significance. A total of approximately 120 subjects will be enrolled and randomized to account for expected rates of premature withdrawal.

Due to uncertainty regarding the expected sham response rate and treatment effect differential, this study will utilize an adaptive design that allows one blinded interim sample size re-estimation after a minimum of 70 subjects have been enrolled and completed treatment. The pre-specified maximum allowable sample size following re-estimation will be 240 enrolled (~184 evaluable).

NEOSYNC, INC.

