10.2 SECONDARY OUTCOMES

Additional outcomes will include the following:

- The change in symptom scores on the HAM-D₁₇ through 6 weeks of treatment
- The change in symptom scores on the MADRS through 6 weeks of treatment.
- Clinical response, defined by 50% or greater reduction on the MADRS total symptom scores following 6 weeks of treatment.
- Effectiveness of blinding questionnaire

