- Submission of knowingly false information from the research facility to the Sponsor, study monitor, or appropriate regulatory authority.

Subjects who withdraw from the study for any reason will not be replaced. Subjects who voluntarily withdraw from the study will be asked to complete the Week 6/Early Termination assessments. Subjects who are withdrawn due to adverse events will be followed until resolution or stabilization of the adverse event.

SAMPLE SIZE

The primary endpoint of the study is clinical response at Week 6, defined by 50% or greater reduction on the Hamilton Rating Scale for Depression (HAM-D¹⁷) from baseline (Day 0). The null and alternative hypotheses of interest are:

$$H_0: \pi_A - \pi_S = 0$$

vs.

$$H_a: \pi_A - \pi_S \neq 0$$

where π_A is the proportion of subjects who show 50% or greater improvement in HAM-D¹⁷ total score from baseline (Day 0) to Week 6 for the active sTMS treatment and π_S is the equivalent value for the sham-controlled group.

The calculation of sample size requirements for this confirmatory study is based on the results observed in the per-protocol (PP) analysis of non-treatment-naïve subjects who completed Week

6 HAM-D¹⁷ assessments in the previous NEST trial NND-3001.

In that population, 34% of subjects treated with active sTMS were categorized as responders, whereas only 8% of sham treated subjects responded. Assuming true population response rates of 34% for sTMS and 8% for Sham, power analysis indicates that a PP sample size of 92 subjects (i.e., 92 subjects, or 46 subjects per treatment group, without major protocol violations and with HAM-D¹⁷ measured at Week 6) yields 81% power to demonstrate superiority of sTMS over Sham, where the statistical test is Fisher's exact test at a two-sided 0.05 level of significance.

The sample size ratio for the active treatment group to sham-controlled group is 1:1. Based on a conservative estimate of published studies, approximately 23% of enrolled subjects may not be part of the PP population in each treatment group. Thus, a total of 120 subjects (60 per group) will therefore be enrolled in the study to account for potential drop-outs and protocol noncompliance prior to Week 6.

SCHEDULE OF VISITS

Table A on the following page displays the schedule of visits and procedures for protocol NND-3002. Full details can be found in the protocol.

TABLE A: STUDY FLOWCHART

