A urine toxicology dipstick screen will be performed at screening visit in order to rule out use of unprescribed psychoactive medications. All subjects with a positive test must be withdrawn from the study unless a subsequent negative test is obtained (this may only occur once prior to randomization). These subjects will be informed that urine samples may be obtained on additional occasions during the study, but will not be told how many samples nor about the time at which the samples will be collected. Sites may conduct an optional urine toxicology screen if the Investigator feels it is indicated at any time during a subject's study participation. Urine Toxicology Screening will be provided in data listings.

K. Other Assessments

1. Concomitant Medications are collected at Baseline and throughout the study through Week 12. All medications prescribed and/or taken by the subject will be collected. Any changes to these medications may be updated at any visit. Concomitant medications will be provided in data listings.

2. Verification of Blinding Questionnaire:

A treatment blinding questionnaire will be administered to treatment administrator ("treaters"), raters and patients at Treatment Day 5 (end of Week 1) and Treatment Day 30 (end of Week 6, or i.e. end of the double-blind phase). This brief questionnaire will ask participants to (a) provide a best guess of the treatment to which the patient was randomized (sTMS or Sham), (b) a reason for the guess (improvement or lack thereof; how the machine operated; something the subject, rater, or treatment administrator did or said; no reason); and (c) confidence level of the guess (Extremely; Considerably; Moderately; Slightly; Not at All).

From the "best guess" and its "confidence level", a blinding index will be calculated at each of Treatment Days 5 and 30, similar to the blinding index discussed in Bang et al. (2004)¹ and Kolahi et al. (2009)². Specifically, for each treater, rater, and patient at each visit, a blinding index will be created as follows:

- If a treater/rater/patient correctly guessed the patient's randomized treatment group AND was extremely or considerably confident in the guess, then **the blinding index will be set to 1** for that treater/rater/patient

¹ Bang H, Ni L, Davis C E. Assessment of blinding in clinical trials. *Controlled Clinical Trials*. 2004; 25: 143-156.

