² Kolahi J, Bang H, and Park J. Towards a proposal for assessment of blinding success in clinical trials: up-to-date review. *Community Dentistry and Oral Epidemiology*. 2009; 37: 477-484.

- If a treater/rater/patient correctly guessed the patient's randomized treatment group AND was moderately or slightly confident in the guess, then **the blinding index will be set to 0.5** for that treater/rater/patient
- If treater/rater/patient was "not at all confident" in their guess, then **the blinding index will be set to 0** for that treater/rater/patient regardless of the treatment group to which the patient was randomized.
- If a treater/rater/patient incorrectly guessed the patient's randomized treatment group AND was moderately or slightly confident in the guess, then **the blinding index will be set to -0.5** for that treater/rater/patient
- If a treater/rater/patient incorrectly guessed the patient's randomized treatment group AND was extremely or considerably confident in the guess, then **the blinding index will be set to -1** for that treater/rater/patient

Descriptive statistics (sample size, mean, standard deviation) of the treater, rater, and patient blinding index are presented at each visit (Treatment Day 5 and Treatment Day 30) for each treatment group and both treatments combined. A mean close to 0 indicates random blinding (or random guessing); a mean closer to 1 than 0 may indicate failure in blinding (majority of "guesses" were correct); a mean closer to -1 than 0 indicates mainly incorrect guesses were made.

L. Study Treatment Administered

A data listing of the study treatment administered will be provided. The cumulative number and percentage of subjects exposed to study treatment by Week, and descriptive statistics of the number of treatments and percentage of planned treatments overall and by each Week, will be provided. This will be presented by double-blind treatment group for each of the double-blind and open-label phases.

The number and percentage of subjects receiving concomitant psychotropic medications and significant non-drug therapy will be summarized by treatment group for the double-blind phase and for the open-label phase.

M. Data Listings

Listings of all data collected on the case report forms will be provided as an appendix to the clinical study report.

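### The blinding-index guide reads possible failure only from a mean above 0.5, so clearly better-than-chance guessing can fall short of it (minor, descriptive)

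*SAP*

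**What the plan says.** SAP section K.2 (Verification of Blinding Questionnaire) asks treaters, raters and patients, at the end of Week 1 and of Week 6, for a best guess of the assigned arm, a reason and a confidence level.

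- For a correct guess at either of the two highest confidence levels, "the blinding index will be set to 1".
- A correct guess that "AND was moderately or slightly confident in the guess" scores 0.5.
- Incorrect guesses mirror these at -1 and -0.5.
- A respondent with no confidence scores 0.

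The sample size, mean and standard deviation are reported at each visit "for each treatment group and both treatments combined". No interval and no proportion correct is planned.

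The guide has three readings. A mean near 0 (no limit given) is random guessing; "a mean closer to 1 than 0 may indicate failure in blinding", explained in brackets as most guesses being correct; and a mean nearer -1 than 0 is mainly wrong guesses. Protocol section 11.5 gives the same guide.

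Blinding is a listed outcome. The Protocol synopsis states "Adequacy of blinding will be assessed using a Blinding Questionnaire administered at the Week 1 and Week 6 clinical assessment visits", and Protocol section 10.2 lists "Effectiveness of blinding questionnaire".

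**The concern.** The failure wording and its bracketed explanation describe different results. When all guesses carry equal non-zero confidence, a majority correct needs only a mean above 0. The wording asks for a mean above 0.5, and the half-weight on less confident guesses makes that stricter still. Results from near 0 up to 0.5 have no stated interpretation, although many of them would be far from chance.

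The primary endpoint is a HAM-D17 score from an interview in a sham-device trial, so the guesses of patients and raters bear on how far the result can be trusted. A report that follows the guide literally could leave clear better-than-chance guessing without comment.

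**Working it through.** **Inputs.** The weights 1, 0.5 and 0 come from SAP K.2. The 46 per arm (92 combined) is the planned per-protocol number in the SAP's Sample Size section. The counts correct, the confidence mixes and independence between guesses are assumptions; the documents give none of them. They also state no value of the index, so there is no plan figure to reproduce.

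**The cut.** A mean m is closer to 1 than to 0 when |m - 1| < |m|, that is, m > 0.5.

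**Proportion correct needed.** Let p be the proportion correct and h the share of guesses at high confidence, the rest moderate or slight. If confidence is unrelated to correctness, the expected mean is (2p - 1)w, with w = h + 0.5(1 - h). Then m > 0.5 requires p > 0.5 + 0.25/w.

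| h | w | p must exceed | Smallest count of 46 |
|---|---|---|---|
| 1 | 1 | 0.75 | 35 |
| 0.5 | 0.75 | 0.833 | 39 |
| 0.25 | 0.625 | 0.90 | 42 |
| 0 | 0.5 | 1.00 | none |

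In the last row, 46/46 correct gives 0.5 × 46/46 = 0.50 exactly, which is not above 0.5.

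If correct guessers are more confident than incorrect ones, with mean weights wc and wi, the condition becomes p > (0.5 + wi)/(wc + wi). Weights (0.75, 0.5) give 0.80, (1, 0.5) give 0.67, and the extreme (1, 0) gives 0.50. So the cut agrees with a bare majority only in that extreme case.

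**Illustrations (t-based intervals on the scores).**

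- One arm, 34/46 correct at high confidence: (34 - 12)/46 = 0.478, SD 0.888, 95% CI 0.21 to 0.74. The exact binomial two-sided p against 50% is 0.0016. The failure reading is not met.
- Combined, 74/92 correct at moderate confidence: 0.5 × (74 - 18)/92 = 0.304, 95% CI 0.22 to 0.39. The failure reading is not met.

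**How often.** Suppose 70% guess correctly in both arms and confidence is unrelated to correctness. The chance that the combined mean exceeds 0.5 is 12% if all guesses are highly confident, about 0.3% if half are, and 0 if none is. The chance that its 95% CI lies above 0 is 96% to 98% in the same three cases.

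**Check on reading the index against 0.** With equal confidence throughout, the combined CI lies above 0 from 56/92 correct.

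- *Shared guess.* If 37/46 in each arm guess active at moderate confidence, the arms give +0.30 and -0.30, and the combined index is 0.00 (-0.10 to 0.10). It is not described as unblinding.
- *Outcome-driven guessing at Week 6.* The SAP plans on "Assuming true population response rates of 34% for sTMS and 8% for Sham". If responders guess active and everyone else guesses sham, 34% of the active arm and 92% of the sham arm are correct, about 16/46 and 42/46. At moderate confidence the combined index is 0.5 × (58 - 34)/92 = 0.13 (0.03 to 0.23). Its CI would lie above 0 about 75% of the time with the device blind intact.

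**The case against.** The strongest reply is that this is a soft reader's guide. It says only that a mean may indicate failure, attaches no action or error rate to 0.5, and sits under Other Assessments, outside the label sequence. Nothing is concealed: the sample size, mean and SD are printed by arm and combined, a reader can compute the interval from them, and SAP section M lists all case report form data. A value of 0.48 would be visible, and the bracketed explanation would itself point a reader of 34/46 towards concern. All of this stands, and it keeps the point minor.

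A reader might go further and infer that the plan would declare 0.48 to be random guessing. The documents do not support that. The limit for a mean near 0 is never defined, so such a value has no stated reading. It would count as random guessing only if near 0 were taken to mean nearer 0 than 1.

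The reply does not remove the mismatch itself. The one stated failure reading disagrees with its own explanation and can leave even perfect guessing at moderate confidence unmet.

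**Conclusion.** The point holds as a minor one. The failure reading in SAP K.2 and Protocol 11.5 requires a mean above 0.5. That corresponds to more than 75% to 90% correct in the mixes shown, or cannot be reached at all, when confidence is unrelated to correctness. It requires less if correct guessers are the more confident ones. Results such as 34/46 at high confidence (0.48) or 74/92 at moderate confidence (0.30) exclude 0 but do not meet it.

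The counts and confidence mixes are illustrations and independence is assumed; only the weights, the cut and the group size come from the documents. It would be wrong to infer that the trial's efficacy inference is weakened. The check is descriptive, and the primary test, alpha, sample size and gatekept secondaries are unaffected.

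**What to change.** In SAP K.2, with matching wording in Protocol 11.5:

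1. Keep the by-arm and combined summaries at both visits.
2. Replace the 0.5 wording with a comparison against 0. Add a 95% CI to each index, and the unweighted proportion correct by arm and respondent type. Describe a combined index whose CI lies above 0 as better-than-chance guessing.
3. Show both arms beside it. Note that opposite signs of similar size suggest a shared guess, while one arm clearly positive with the other near 0 is still discrimination.
4. At Week 6, also show the index by the reason given, because guesses can follow outcome. The questionnaire already collects "a reason for the guess (improvement or lack thereof; how the machine operated" among its options.
5. Treat every reading as descriptive.

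Do not require both arms to be positive, and do not rule out concern that rests on one arm. With 90% correct on active and 50% on sham, requiring a lower limit above 0 in each arm (at least 30/46) would detect the problem about 2.7% of the time per respondent type. The combined index detects it 98.7% of the time. At high confidence the present guide flags the active arm 99.8% of the time.

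The cost is SAP wording and a few table columns from data already collected. Intervals for raters and treaters should be labelled approximate, since they guess for several patients.
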